### 9.6.7 Safety Analysis

Treatment-emergent AEs are defined as events with an onset date on or after the start of the first pegloticase infusion through 30 days after the last dose of pegloticase. AEs that occur more than 30 days after the last dose of pegloticase through the 3-month follow-up visit will also be summarized.

The number and percentage of subjects experiencing AEs will be summarized by system organ class and preferred term. Summaries by maximum severity and relationship to study drug will also be provided. SAEs and AEs leading to discontinuation of study drug will be presented by system organ class and preferred term. The proportion of subjects with each AESI will also be summarized.

Laboratory test results will be summarized by study visit and change from baseline. Shift tables for laboratory parameters by Common Terminology Criteria for Adverse Events grade will be presented. Laboratory test results will also be classified relative to the normal reference range (normal, low, or high).

Vital signs, including BP, respiratory rate, temperature, and heart rate, will be summarized by study visit and change from baseline.

Prior and concomitant medications will be summarized and/or included in the data listings.

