#### 12.3.1 Definition of Period of Onset

- Non-treatment-emergent events:

This document is confidential.

- Adverse events with an onset date and time strictly prior to the first pegloticase treatment.
- Treatment-emergent adverse events (TEAEs):
  - Adverse events that occur on or after the start date and time of the first pegloticase infusion through 30 days after the last dose of pegloticase.
- Adverse events in the follow-up period:
  - Adverse events with an onset date more than 30 days after the last dose of pegloticase.

Missing data conventions for AEs are described in [Section 8.3.2](#). The imputed onset dates will be used to determine the period of onset.

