### 12.3.2. Presentation of Results

All AEs, both serious and non-serious, will be assessed for severity using the Rheumatology Common Toxicity Criteria (CTC) v2.0. Summaries of TEAEs will be for the safety population.

An overall summary of TEAEs will be provided, including the number and percentage of subjects with each AE type as well as the number of events for each of the following:

- TEAEs
- Serious TEAEs
- TEAEs related to pegloticase
- Serious TEAEs related to pegloticase
- TEAEs with a Rheumatology CTC Criteria of 3 or higher
- TEAEs leading to permanent withdrawal of pegloticase
- TEAEs related to pegloticase leading to permanent withdrawal of pegloticase
- TEAEs leading to death
- TEAEs of special interest

Using the safety population, an overall summary of AEs occurring during the follow-up period (with onset more than 30 days after the last dose of study medication), including the number and percentage of subjects with each AE type as well as the number of events for each of the following:

- AEs
- Serious AEs
- AEs with a Rheumatology CTC Criteria of 3 or higher
- AEs leading to death
- AEs of special interest

This document is confidential.

Percentages for the overall summary of AEs during follow-up will be based on the number of subjects who had follow-up more than 30 days after last dose of medication.

Additional AE summaries will be provided by onset period, including the number, percentage of subjects, experiencing TEAEs for the following:

- TEAEs overall and by SOC and PT for the: Pegloticase Treatment Period and Follow-up Period
- TEAEs by maximum severity, overall and by SOC and PT for the Pegloticase Treatment Period
- TEAEs related to pegloticase overall and by SOC and PT for the Pegloticase Treatment Period
- TEAEs related to pegloticase by maximum severity, overall and by SOC and PT for the Pegloticase Treatment Period
- Serious TEAEs, overall and by SOC and PT for the: Pegloticase Treatment Period and Follow-up Period
- TEAEs leading to permanent withdrawal of pegloticase, overall and by SOC and PT for the Pegloticase Treatment Period

The incidence per person years of exposure to pegloticase will be provided on all tables except those summarizing events by maximum intensity, and those for the post-treatment follow-up period.

Person years of exposure to pegloticase is defined as  $[(\text{last treatment date in the period} - \text{first treatment date in the period} + 1)/365.25]$ .

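### SAP 12.3.2 fills the follow-up AE and SAE tables by SOC and PT with treatment-emergent events, which under SAP 12.3.1 cannot have onset in follow-up, so both tables are empty as written

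*SAP*

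**What the plan says.** SAP 12.3.1 sorts adverse events by onset. Events before the first infusion are non-treatment-emergent. Treatment-emergent events (TEAEs) are "Adverse events that occur on or after the start date and time of the first pegloticase infusion through 30 days after the last dose". Events in the follow-up period are "Adverse events with an onset date more than 30 days after the last dose of pegloticase".

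SAP 12.3.2 then describes two sets of outputs that involve follow-up:

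- An overall count summary, specified as "an overall summary of AEs occurring during the follow-up period (with onset more than 30 days after the last dose of study medication"). Its rows are AEs, serious AEs, Grade 3 or higher, deaths and events of special interest. Its percentages use subjects who were followed beyond 30 days after the last dose.
- By-term tables, introduced by "Additional AE summaries will be provided by onset period, including the number, percentage of subjects, experiencing TEAEs for the following". Two entries name the follow-up period: "TEAEs overall and by SOC and PT for the: Pegloticase Treatment Period and Follow-up Period" and "Serious TEAEs, overall and by SOC and PT for the: Pegloticase Treatment Period and Follow-up Period".

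Protocol 9.6.7 uses the same 30-day cut for treatment emergence and adds that "AEs that occur more than 30 days after the last dose of pegloticase through the 3-month follow-up visit will also be summarized".

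**The concern.** The by-term follow-up entries ask for events that are treatment-emergent and also have onset in follow-up. SAP 12.3.1 makes those two classes adjacent and exclusive. A program that applies both flags as defined returns no rows, while the overall follow-up summary next to it can show events.

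What is at stake is the general tabulation of late events by system organ class and preferred term. Subjects who stop infusions early are meant to stay on study through Week 24 (Protocol 9.3.3.1.1), and AEs are collected to the 3-month visit, so a good part of an early stopper's observation counts as follow-up. Safety 3 months after treatment is a stated objective (Protocol 8, SAP 3.3). Biopsy-proven rejection is a safety endpoint collected through AE recording (Protocol 9.5.4.1.1.6), and the readable part of SAP 12 describes no separate table for it. SAP 10.4 is largely redacted and the index of tables (SAP 18) is not in the available text, so a dedicated table elsewhere cannot be ruled out.

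**Working it through.** The plan states no figure on this point, so there is nothing to reproduce. The check is one of definitions, followed by day counts to show which part of observation is affected.

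**Inputs.** The period rules are in SAP 12.3.1. The target days are in SAP 8.4, Table 1: Week 2 = Day 15, Week 4 = Day 29, Week 8 = Day 57, Week 12 = Day 85, Week 22 = Day 155, Week 24 = Day 169. Let *L* be the day of the last infusion and *d* the onset day, with the first infusion on Day 1.

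**Step 1: overlap.** TEAE means 1 ≤ *d* ≤ *L* + 30. Follow-up means *d* > *L* + 30. No *d* meets both conditions. A day-by-day classification of example subjects (two completer scenarios, last infusion at Week 4, last infusion at Week 12) gave 0 days in both classes and 0 days in neither.

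**Step 2: days affected.** Follow-up days up to Week 24 = 169 − (*L* + 30).

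| Last infusion | *L* | TEAE window ends | Follow-up days to Day 169 | Share of 169 |
|---|---|---|---|---|
| Week 2 | 15 | Day 45 | 124 | 73% |
| Week 4 | 29 | Day 59 | 110 | 65% |
| Week 8 | 57 | Day 87 | 82 | 49% |
| Week 12 | 85 | Day 115 | 54 | 32% |

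For a completer, 155 + 30 = 185, so follow-up starts on Day 186. Taking three months as 91 days (an assumption), a visit timed from Week 24 falls on Day 169 + 91 = 260 and gives 260 − 185 = 75 follow-up days. A visit timed from the last infusion falls on Day 155 + 91 = 246 and gives 246 − 185 = 61. Both are shown because the protocol describes the timing of this visit in both ways. As specified, the two by-term follow-up tables cover none of these days.

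**Step 3: could another rule in the SAP fill the tables?**

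- *Gout flares (SAP 12.3.3.3).* This section counts the 30 days after the end of treatment as follow-up. Carried over to 12.3.2, with the end of treatment taken as the last infusion, it would create 30 overlapping days (Days 156 to 185 for a completer) and still omit everything later. It governs the flare summary only, and 12.3.2 restates its own 30-day boundary.
- *Partial dates (SAP 8.3.2.1).* Where only part of the onset date is known, treatment emergence is judged against the first infusion alone, while SAP 12.3.1 uses the imputed date to assign the period. An event imputed to a date beyond *L* + 30 could therefore carry both flags. That would put a stray event in the table; it would not make the table valid. It is also why the conclusion is limited to events with a complete onset date.

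**The case against.** The strongest reply is that this is a label slip with an obvious intent. The tables are described as being by onset period, SAP 12.3.1 defines a follow-up onset period, the overall follow-up summary already uses AEs, and SAP 12.3.2 exempts follow-up tables from person-year rates, which makes sense only if they are expected to hold events. In a 20-subject study, an empty by-term table beside a non-empty overall summary would be noticed. The intent is indeed clear, and that keeps the point small. It does not remove it: a programmer should not have to override a written definition, and two programmers could resolve it differently.

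A reader might go further and infer that late events vanish from the report, or that no table would say what they were. The documents do not support that. SAP 12.3.2 requires separate listings of all AEs, serious AEs, events of special interest, events leading to withdrawal and deaths, each marked with treatment emergence and period of onset. The summaries of special-interest events are not limited to TEAEs: infusion reactions and anaphylaxis include a category beyond 24 hours after infusion, cardiovascular events are tabulated by SOC and PT (both sets only if at least 5 subjects are affected), and flares are summarised by month.

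A reader might also infer a breach of Protocol 9.6.7. Its sentence on late events requires that they be summarised and does not explicitly require this by term. The overall follow-up summary meets that wording; the by-term follow-up tables are the SAP's own commitment.

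**Conclusion.** The inconsistency is real and lies in operative SAP text. As written, the follow-up AE and serious AE tables by SOC and PT contain no event with a complete onset date. The consequence is confined to these two general by-term tables. Data capture, the overall follow-up counts and the listings are unaffected, and some events of special interest remain visible in their own summaries.

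The day counts show which part of observation falls outside the tables: 32% to 73% of the time to Week 24 for the early stoppers used as examples, and everything after Day 185 for completers. They rest on target visit days, on chosen stopping times and, for completers, on a 91-day three-month interval. The documents do not say how many subjects will stop at each time, so these percentages must not be read as a share of events lost. The conclusion about the definitions does not depend on any of these assumptions.

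**What to change.** In SAP 12.3.2:

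- For the Follow-up Period, replace the TEAE and serious TEAE entries with AEs and serious AEs whose onset is later than 30 days after the last dose, overall and by SOC and PT. Leave the treatment-period entries as TEAEs.
- Amend the lead-in to these summaries so that it covers follow-up AEs as well as TEAEs.
- State that percentages in the follow-up by-term tables use the denominator already given for the overall follow-up summary, namely subjects with follow-up beyond 30 days after the last dose. At present that denominator is stated only for the overall summary.

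The cost is a few lines of SAP wording and one changed filter in the table program. It needs no new data and has no effect on study conduct or on the efficacy analyses.

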### 12.1 Extent of Exposure

Study drug exposure will be summarized using the duration of treatment (in days), number of doses, and total dosage received for pegloticase. Interruptions in pegloticase infusions will be summarized. Reasons for infusion interruptions will be provided in the listings.

For the Pegloticase Treatment Period, the following will be summarized:

- Pegloticase
  - Number of pegloticase infusions received overall (summarized with frequency summary along with descriptive statistics of mean, SD, median, minimum, and maximum)
  - Duration in days between first and last pegloticase infusion, defined as last infusion date – first infusion date + 1 (summarized with descriptive statistics of mean, SD, median, minimum and maximum)
  - Number of incomplete infusions received (summarized with frequency summary along with descriptive statistics of mean, SD, median, minimum and maximum)
  - Number of interrupted infusions (summarized with frequency summary along with descriptive statistics of mean, SD, median, minimum and maximum)
- At each scheduled Pegloticase infusion visit
  - Number of subjects receiving a complete infusion (i.e. full dose administered)
  - Number of infusions administered without interruption
  - Number of subjects with an interrupted infusion

The usage of prophylaxis treatments (IR prophylaxis usage of fexofenadine in the evening prior to pegloticase infusion, IR prophylaxis of fexofenadine, acetaminophen, and methylpredisone on the morning prior to pegloticase infusion) will be provided in listings only.

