For summaries by SOC, PT, and maximum severity, a subject will only be counted once for each SOC based on the maximum intensity level reported for that SOC and once for each unique PT within that SOC level at the maximum intensity level reported for that PT. For summaries by SOC and PT only, a subject will be counted at most once at the SOC level and at most once at each unique PT within the SOC level. Summaries presenting the frequency of TEAEs by SOC and PT will be ordered alphabetically by SOC and then, within a SOC, alphabetically by PT.

In addition to the listing of all AEs, separate listings will be provided for serious AEs, AEs leading to withdrawal of pegloticase, AEs leading to study discontinuation, AEs of special interest, and AEs leading to death. TEAEs and the period of onset will be identified on each listing. A listing of any subject with an interruption in treatment of pegloticase due to COVID-19 will be created which will identify AEs as pre-interruption, during interruption, or post-interruption.

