#### 12.3.3.1. *Infusion Reactions (IRs) and Anaphylaxis*

An IR will be defined as any infusion-related AE or cluster of temporally-related AEs, not attributable to another cause, which occur during the pegloticase infusion and for up to 2 hours post infusion. Other AEs that occur outside of the 2-hour window following the infusion may also be categorized as an IR at the PI's

This document is confidential.

discretion. Signs and symptoms of the IR and treatments administered will be documented in the medical record and in the eCRF, and will be adjudicated.

Examples of AEs not considered possible IRs include, but are not limited to: laboratory abnormalities that are unlikely to have occurred during or within 2 hours following the infusion (e.g., anemia), gout flares, most infectious diseases, or the recurrence or worsening of a known chronic medical problem identified in the subject's medical history.

The signs and symptoms associated with each event are entered on the eCRF and will be coded with the MedDRA dictionary.

Any incidence of anaphylaxis should be reported as an SAE. Anaphylaxis will be defined using the National Institute of Allergy and Infectious Diseases/Food Allergy and Anaphylaxis Network (NIAID/FAAN) criteria [Sampson et al, 2006] , and will be adjudicated:

1. Acute onset of an illness (minutes to several hours) with involvement of the skin, mucosal tissue, or both (e.g., generalized hives; pruritus or flushing; urticaria, and angioedema (of lips, tongue, or uvula) and  $\geq 1$  of the following:
  - a. Respiratory compromise (e.g., dyspnea, wheeze-bronchospasm, stridor, reduced peak expiratory flow, hypoxemia); and
  - b. Reduced blood pressure or associated symptoms of end-organ dysfunction (e.g., hypotonia [collapse], syncope, incontinence).
2. Two or more of the following that occur rapidly after exposure to a likely allergen for that subject (minutes to several hours):
  - a. Involvement of the skin-mucosal tissue (e.g., generalized hives, itch-flush, swollen lips-tongue, uvula);
  - b. Respiratory compromise (e.g., dyspnea, wheeze-bronchospasm, stridor, reduced peak expiratory flow, hypoxemia);
  - c. Reduced blood pressure or associated symptoms (e.g., hypotonia [collapse], syncope, incontinence); and
  - d. Persistent gastrointestinal symptoms (e.g., crampy, abdominal pain, vomiting).

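### SAP 12.3.2 rates per person-year count TEAEs through 30 days after the last dose but stop person-time at the last infusion, and do not say whether events or subjects are counted

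*SAP*

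**What the plan says.** - **Numerator window.** SAP 12.3.1 treats an event as treatment-emergent if it occurs "on or after the start date and time of the first pegloticase infusion through 30 days after the last dose of pegloticase". The follow-up period begins only after that, so the 30-day tail belongs to the TEAE period.
- **Person-time.** SAP 12.3.2: "Person years of exposure to pegloticase is defined as" last treatment date minus first treatment date plus 1, divided by 365.25. SAP 12.1 applies the same expression to infusion dates when it summarises "Duration in days between first and last pegloticase infusion". Person-time therefore ends on the day of the last infusion.
- **Where the rate appears.** SAP 12.3.2: "The incidence per person years of exposure to pegloticase will be provided on all tables except those summarizing events by maximum intensity". Tables covering follow-up after treatment are also exempt.
- **What is counted.** The overall TEAE summary gives subjects "as well as the number of events for each of the following". In the SOC and PT tables, "a subject will be counted at most once at the SOC level and at most once at each unique PT within the SOC level". Neither statement mentions the person-year rate, and no rule ends a subject's person-time at a first event.

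**The concern.** A rate needs its numerator and denominator to cover the same time. Here the numerator window is 30 days longer than the denominator for every subject, and no section of the SAP adds those days back.

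The excess is not a fixed factor that a reader could divide out. It equals 30 divided by the mean days of exposure, so it grows as subjects stop earlier. Early stopping is built into the design: the sUA rule can end infusions from the Week 4 visit, leaving Week 2 as the last infusion. Adjusting for exposure should make different treatment durations comparable, whereas this formula makes the rate depend on duration. SAP section 14 says the populations were redefined to ease integration with other pegloticase studies, and rates that shift with the stopping mix would not integrate well.

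The unstated counting unit adds a second problem. If subjects are counted, those who have had the event keep accruing person-time, which pulls the rate down. The two errors then work against each other, and the net direction depends on how common the term is.

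**Working it through.** The documents state no person-year total or rate, so there is no plan figure to reproduce. The check applies the SAP formula and compares it with the TEAE window.

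**Inputs**
- N = 20 (SAP 4.1).
- Last infusion at Week 22, target Day 155 (SAP 8.4, Table 1), with a ±3-day visit window (schedule of assessments), giving Day 152 to Day 158.
- Tail of 30 days (SAP 12.3.1), taken as fully observed.
- The numbers stopping early, and when, are assumptions.

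**One subject**

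SAP person-days = d, where d is the inclusive count of days from first to last infusion. The TEAE window is d + 30 days. The overstatement of an event-based rate is (d + 30)/d.

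- Full course: 185/155 = 1.19 (30/158 = 19.0% to 30/152 = 19.7% across the visit window).
- Last infusion Week 4 (Day 29): 59/29 = 2.03.
- Last infusion Week 2 (Day 15): 45/15 = 3.0.
- One infusion only: 31/1 = 31.

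**Cohort, events counted**

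| Scenario | SAP days | TEAE-window days | Overstatement |
|---|---|---|---|
| All 20 complete | 20×155 = 3,100 | 3,100 + 600 = 3,700 | +19% |
| 14 complete, 6 stop at Day 71 (assumed) | 2,170 + 426 = 2,596 | 3,196 | +23% |
| 14 complete, 6 stop at Day 29 (assumed) | 2,170 + 174 = 2,344 | 2,944 | +26% |
| 10 complete, 10 stop at Day 15 (assumed) | 1,550 + 150 = 1,700 | 2,300 | +35% |

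If all complete, person-years are 3,100/365.25 = 8.49 against 3,700/365.25 = 10.13. Ten events give 10/8.49 = 1.18 instead of 10/10.13 = 0.99 per person-year.

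These ratios compare the SAP rate with a rate over the TEAE window. They are ratios of person-time, so they need no assumption about when events occur.

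**Cohort, subjects counted, no censoring at first event**

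Assume a constant hazard h. With all subjects completing, incidence over the window is p = 1 − exp(−185h), so h = −ln(1 − p)/185. The SAP rate is p/155. The ratio to the true rate is therefore (185/155) × p/[−ln(1 − p)].

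| Incidence p | SAP rate / true rate |
|---|---|
| 10% | 1.194 × 0.100/0.1054 = 1.13 |
| 20% | 1.194 × 0.200/0.2231 = 1.07 |
| 31% | 1.00 |
| 50% | 1.194 × 0.500/0.6931 = 0.86 |
| 70% | 1.194 × 0.700/1.2040 = 0.69 |

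The point where the two errors cancel is p = 30.6% if all complete. It is 33.1% in the 14/6 Day 29 mix and 35.4% in the 10/10 Day 15 mix. These two solve the same equation with p averaged over completers and stoppers.

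Adding the 30 days without censoring at first event removes the factor 185/155. That leaves 0.100/0.1054 = 0.95 at 10% incidence and 0.500/0.6931 = 0.72 at 50%. A subject-based rate needs both corrections.

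**The case against.** **The label is explicit.** The SAP calls the denominator exposure and prints the formula, so a reader can see its basis, and no stated figure is miscalculated. That is true: this is a mismatch of definitions, not an arithmetic slip. Labelling the denominator still does not give the tail events any person-time.

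**The tail may carry fewer events.** Relative to the on-treatment rate, a tail rate half as high gives 9.7% in completers, and an empty tail gives no inflation. This limits the effect for some terms. Infusion reactions are defined as events "which occur during the pegloticase infusion and for up to 2 hours post infusion", apart from later events classed as such at the investigator's discretion, so few fall in the tail. Flares were more frequent in Months 1 to 3 of the Phase 3 studies (Protocol 7.1.2), so completers would see less than 19% on that comparison. Against the TEAE window, which is what the tables count, the ratio stays at 185/155.

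**The counting unit can be inferred.** The SOC and PT tables show numbers and percentages of subjects and count each subject once, so subjects is the natural reading there. The overall summary is where the ambiguity is sharpest. The available SAP text ends at section 17, so any table shells or footnotes that settle the unit cannot be seen. This part is accordingly secondary. Even on the subject reading, the rule that ends person-time at first event is missing.

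**The practical effect is modest.** The study has one arm, 20 subjects and no formal testing, and Protocol 9.6.7 promises counts and percentages only. In the ten-event example, 0.99 lies well inside an exact Poisson 95% interval of 0.57 to 2.17 around 1.18. This stands as a limit on importance. Imprecision is no reason to keep a known bias that is cheap to remove.

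**Conclusion.** The concern holds. As written, event-based rates are too high relative to the TEAE window: by 19% if everyone completes on schedule, and by 23% to 35% in the assumed early-stopping mixes. This assumes all 30 tail days are observed; death or loss within them would shrink the excess. Under a constant hazard, subject-based rates are too high for uncommon terms and too low for common ones, crossing at an incidence of about 31% to 35%. A reader therefore cannot correct them with a single factor.

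Counts and percentages of subjects are not touched. The rates are descriptive, so no trial conclusion turns on them, but safety is a stated objective and they go on most TEAE tables. The SAP should be corrected before those tables are produced.

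**What to change.** In SAP 12.3.2:

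1. Define person-years at risk for TEAE rates as [min(last infusion date + 30, last contact date) − first infusion date + 1]/365.25.
2. State whether each rate counts events or subjects. If subjects, end each subject's person-time at the first event of that term.
3. Keep the first-to-last-infusion duration for the exposure table in 12.1, and do not reuse it as the TEAE denominator.

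Restricting the rate's numerator to the first-to-last-infusion dates would also align the two windows. However, the rate would then omit events that the same table counts as TEAEs.

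SAP 12.3.3.3 places the 30 days after treatment in the follow-up period for gout flares, unlike 12.3.1. It should be aligned at the same time.

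In the text, the cost is one formula and a sentence or two on counting and censoring. Infusion, contact and onset dates are already collected, and trial conduct does not change. If subjects are counted, programming must also derive a separate denominator for each SOC, PT and event category.

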### 9.4 Treatments

#### 9.4.1 Treatments Administered

Starting at the Day 1 visit, subjects will receive pegloticase at a dose of 8 mg administered IV every 2 weeks for a total of 12 infusions from Day 1 through the Week 22 Visit.

After the Week 24 Visit, subjects should resume regular care for gout per the judgment of the treating physician, including resumption of ULT upon pegloticase discontinuation, if appropriate. Subjects will have a 3-month Follow-up visit to assess clinical status, including sUA levels.

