#### **14. Changes from Analysis Planned in Protocol**

The analysis population definitions have been changed:

- Per the protocol, only the modified Intent-to-Treat (mITT) population was defined as all subjects who receive at least 1 dose of pegloticase. The mITT population was planned to be used for analysis of ADA, efficacy and safety data.
- For the purposes of ease of future integration with other pegloticase studies, the mITT definition has been removed, and instead has been replaced by the Intent-To-Treat (ITT) population definition (for the analysis of ADA and efficacy data) and the safety population definition (for the analysis of safety data). Both the ITT and the safety population are defined as all subjects who receive at least 1 dose of pegloticase.

The phrasing of the safety endpoints relating to laboratory tests and vital signs has been updated from "Laboratory tests" and "Vital signs" to "Laboratory tests: change from baseline to each scheduled assessment" and "Vital signs: change from baseline to each scheduled assessment," respectively.

This document is confidential.

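### SAP 12.3.2 prints an adverse event incidence per person-year with no defined numerator and no censoring at first event; if the tables' subject counts are used, it is not a valid rate for common or early events.

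*SAP*

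**What the plan says.** SAP 12.3.2 defines the rate column in pieces:

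- **Where it appears.** "The incidence per person years of exposure to pegloticase will be provided on all tables except those summarizing events by maximum intensity". The tables for the post-treatment follow-up period are also exempt.
- **Denominator.** "Person years of exposure to pegloticase is defined as" the last treatment date minus the first, plus 1, divided by 365.25. Nothing stops a subject's clock at a first event.
- **What the SOC/PT tables contain.** "Additional AE summaries will be provided by onset period, including the number, percentage of subjects, experiencing TEAEs for the following". No event count is listed for them.
- **How subjects are counted there.** "For summaries by SOC and PT only, a subject will be counted at most once at the SOC level", and likewise at most once for each preferred term.
- **The overall summary differs.** It is planned as "including the number and percentage of subjects with each AE type as well as the number of events".

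SAP 12.3.1 sets the period over which treatment-emergent events are counted: "on or after the start date and time of the first pegloticase infusion through 30 days after the last dose of pegloticase". Protocol 9.4.1 plans "a total of 12 infusions from Day 1 through the Week 22 Visit", and SAP Table 1 puts the Week 22 target at Day 155.

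Neither document says whether the rate's numerator is subjects or events.

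**The concern.** On the SOC/PT tables the only count on display is subjects, so a programmer would most naturally divide that count by total person-years. A subject whose first event comes in Week 2 can then never count again for that term, yet keeps adding exposure to its denominator until the last infusion. The column would carry no information on timing or recurrence beyond the percentage printed beside it.

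The rows most affected are those where many subjects have an event, or have it early: the any-event row, broad SOC rows, and possibly gout flares. Flares are recorded as adverse events, and Protocol 7.1.2 reports a higher flare rate on pegloticase in Months 1 to 3 of the Phase 3 studies. A reader who took the column for an incidence rate would misread those rows and could not safely set them beside rates from a study of different length.

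**Working it through.** Neither document states an adverse event rate, so there is no figure of the plan's own to reproduce.

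**Inputs from the documents**
- Exposure with 12 on-schedule infusions: 155 days (SAP 12.3.2 definition, SAP Table 1). T = 155/365.25 = 0.4244 years; for 20 subjects, 8.49 person-years.
- Treatment-emergent window for the same subject: 155 + 30 = 185 days (SAP 12.3.1). W = 185/365.25 = 0.5065 years.
- Infusion reactions in Phase 3: 22/85, 26% (Protocol 7.1.2).

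**Assumptions.** A subject-count numerator; a constant hazard unless stated otherwise; cumulative incidence p over the 185 days. The documents give no flare percentage and no share of early stoppers, so ranges are shown.

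**1. Ceiling (no hazard assumption).** Printed rate = p/T. At p = 1 this is 365.25/155 = 2.36 per person-year. If all 20 subjects have a term, the table prints 2.36 whether onset was Day 2 or Day 150, and whether each had one episode or ten. In general the ceiling is 1 divided by mean exposure in years.

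**2. Size under the SAP's own windows.** First-event rate = -ln(1-p)/W.

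| p | Printed, p/T | First-event rate | Printed is |
|---|---|---|---|
| 10% | 0.24 | 0.21 | 13% too high |
| 26% | 0.61 | 0.59 | 3% too high |
| 50% | 1.18 | 1.37 | 14% too low |
| 80% | 1.89 | 3.18 | 41% too low |
| 90% | 2.12 | 4.55 | 53% too low |

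Two errors oppose each other. Counting events for 185 days over 155 days of exposure inflates the rate by a factor of 185/155 = 1.19; failing to censor deflates it by p/(-ln(1-p)). They cancel where p/(-ln(1-p)) = 155/185, at p of about 31%. The shortfall passes one half only above about 88%.

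**3. Early events (assumed: 16 of 20 affected, mean first event at day 45).**
- Printed: 16/8.49 = 1.89.
- Censored at first event, otherwise followed to day 185: (16 × 45 + 4 × 185)/365.25 = 1,460/365.25 = 4.00 person-years, so 16/4.00 = 4.00 per person-year.
- 1.89/4.00 = 0.47, or 53% too low.

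**4. Early stoppers.** Suppose 30% or 50% of subjects have their last infusion at day 15 or day 43, with window and exposure shortened to match. A hazard of 0.3 per person-year is then overstated by 16% to 27%, a hazard of 1 by 0% to 10%, and a hazard of 3 is understated by 22% to 32%.

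**5. Dependence on length.** At a constant hazard of 3 per person-year, the printed rate is (1 - exp(-3 × (d + 30)/365.25))/(d/365.25) for d days of exposure: 2.75 at 78 days, 1.84 at 155 and 0.96 at 365.

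**The case against.** **The numerator is inferred.** This stands. The count-once rule governs how subjects are tallied and is silent on the rate. On the overall summary, which carries event counts, events over uncensored exposure would be a legitimate event rate apart from the 30-day mismatch. For the SOC/PT tables subjects are the natural reading, but the SAP does not say so.

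**Most rows are uncommon events, and those err the other way.** This also stands. A reader might infer that every rate is understated, or that half is the limit of the understatement. The documents support neither. Below about 31% affected the printed rate is too high, which includes the 26% that the protocol quotes for infusion reactions. The size above that point depends on frequencies and timings the documents do not give.

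**The key events are summarised elsewhere.** Partly. Gout flares get counts per subject and by month (SAP 12.3.3.3). Infusion reactions get a Kaplan-Meier plot, and per-infusion counts if at least 5 subjects have events (SAP 12.3.3.1). Other terms, apart from their percentages and listings, have no such backstop.

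**Nothing is decided on this column.** Correct. The study is single-arm, and Protocol 9.6.5 plans no formal testing.

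**Integration.** A reader might infer that the rate defeats the purpose in SAP 14, "For the purposes of ease of future integration with other pegloticase studies". That phrase explains why the analysis populations were renamed; it says nothing about pooling adverse event rates.

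**Censoring does not remove length dependence when events cluster early.** True. In the day-45 example, 351 days of exposure plus 30 would give 16/((16 × 45 + 4 × 381)/365.25) = 2.60, against 4.00 here. The censored figure is still a proper first-event rate over a stated period; the printed one is not.

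**Conclusion.** The point holds as a defect of definition. SAP 12.3.2 names a rate, fixes an uncensored denominator that ends 30 days before the event window does, and leaves the numerator open. If the subject counts on the SOC/PT tables are used, the result is the percentage affected divided by mean exposure. The ceiling of 2.36 per person-year rests only on that numerator and 12 on-schedule infusions.

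The sizes rest on more: a constant hazard and full treatment for the 41% and 14% shortfalls and the 13% excess, and an assumed 16 of 20 affected at a mean of day 45 for the 53%. The direction changes at about 31% affected, so rows of one table would err in opposite directions and could not be compared with each other. The consequence is limited to descriptive reporting, but the correction is cheap and should be made before the tables are produced.

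**What to change.** In SAP 12.3.2, state the numerator for each table that carries a rate, and then:

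- **Tables that count subjects:** divide the subjects with at least one event by person-time from first infusion to that subject's first event of that SOC or PT. For a subject without an event, run the time to the end of the treatment-emergent window (last dose plus 30 days, or end of follow-up if earlier).
- **Tables where full person-time is kept:** use the number of events as numerator, run person-time over the same treatment-emergent window, and label the column *events per person-year*.

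The cost is SAP wording and, for the first option, denominators specific to each term in the adverse event program. No new data are needed. Printed rates for common events will rise, and those for uncommon events will fall slightly once the windows match.
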